### 323 Missing data

324 If a patient remained in the study for less than 365 days for reasons other than death, the  
325 following imputation methods will be applied:

- 326 1. Proportional Fraction. The proportion of DAOH will be calculated for the period the patient  
327 was on study and multiplied by 365;
- 328 2. Worst case scenario. Days not on study will be counted as NOT alive/out of hospital;
- 329 3. Best case scenario. Days not on study will be counted as alive and out of hospital.

330

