#### 226 Education

227           Education program is designed and run by the TR team. Patients will be taught how to self-  
228 evaluate, how to measure HR, blood pressure, body mass, how to performed all modalities of exercise  
229 training, how to evaluate the level of perceived exertion according to the Borg scale and how to  
230 operate a TR set. Education will also encompass nutritional counselling, lipid management, smoking  
231 cessation, vocational and psychosocial support.

232

233 **Control Group**

234 Patients randomized to the CG will undergo baseline clinical examinations during a 3-day  
235 hospitalisation and then will be under observation until the end of the 9th week and will receive usual  
236 care appropriate for their clinical status and standardized within a particular center (some of them can  
237 participate in a rehabilitation program and some of them has remote monitoring of CIEDs). After the  
238 9th week patients will undergo final assessments during a 3-day hospitalization.

239 All patients, regardless of the treatment group, will receive recommendations for suitable  
240 lifestyle changes and self-management according to guidelines.

241

242 **Clinical examinations**

243 All 850 patients will undergo the following assessments at entry (during 5 days of  
244 hospitalization-TRG, and 3 days of hospitalisation-CG) and after completing the 9-week program  
245 (during 3 days hospitalisations – both groups): clinical examination with symptom evaluation (NYHA  
246 class), blood testing [blood count, serum creatinine, electrolytes (sodium, potassium), glycaemia, N-  
247 terminal pro B-type natriuretic peptide (NT-proBNP), aspartate aminotransferase, alanine  
248 aminotransferase, thyroid stimulating hormone (TSH), international normalized ratio (INR),  
249 urinalysis], ECG, two-dimensional echocardiography, six-minute walk test (6-MWT), CPET, 24 hours  
250 holter ECG monitoring, evaluation of CIEDs proper functioning, and psychological assessment: the  
251 QoL based on SF-36 Survey; the depression based on Beck inventory; the anxiety based on STAY.  
252 Additionally, after 9 weeks, the TRG will be analyzed for: safety and patients' acceptance of and  
253 adherence to hybrid comprehensive TR.

254

255 **Evaluation of novel model of hybrid comprehensive telerehabilitation in terms of tertiary**  
256 **analyses**

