### 299 **Primary hypothesis sample size considerations**

300 The primary study hypothesis is that TRG strategy is superior to CG strategy resulting in a  
301 larger percent of DAOH. Because possible follow-up varies between patients (12 to 24 months after  
302 the 9-week training period), the primary analysis will rely on the percent of DAOH calculated as the  
303 ratio of the DAOH divided by total days of follow-up for each patient.

304 The sample size for this study is calculated assuming 1:1 treatment allocation ratio, and an  
305 overall two-sided level of significance  $\alpha = 0.05$ . Mean difference in the number of DAOH for the  
306 TRG arm and the CG arm is 21 days with a common standard deviation in each arm of 100. The  
307 Wilcoxon-Mann-Whitney test with the above assumptions and with a sample size of 400 evaluable  
308 subjects per study arm (a total of 800) yields 80% power to declare the observed difference as  
309 statistically significant. Accounting for a 5% loss to the follow-up, the total number increases to 842.

310

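### Worst-case and best-case imputation name no arm, so they do not bracket the treatment difference, and the proportional rule stretches unequal required entry stays over a year in ITT

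*Protocol*

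**What the plan says.** The Missing data section opens "If a patient remained in the study for less than 365 days for reasons other than death, the" and then lists three imputation rules:

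- Rule 1: "Proportional Fraction. The proportion of DAOH will be calculated for the period the patient" was on study, multiplied by 365.
- Rule 2: "Worst case scenario. Days not on study will be counted as NOT alive/out of hospital".
- Rule 3: "Best case scenario. Days not on study will be counted as alive and out of hospital".

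No rule mentions a treatment arm, and none is designated for the primary analysis.

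Four other places bear on how the rules behave.

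- **Primary Outcome** (Statistical Analyses) subtracts the days of every hospitalization. It starts ITT follow-up at randomization and MITT follow-up when the nine weeks end.
- **Table 8** defines a hospitalization by overnight stay and length. It makes no exception for stays that the study itself requires.
- **Clinical examinations** puts the TR arm in hospital for 5 days at entry, and the sentence continues "hospitalization-TRG, and 3 days of hospitalisation-CG) and after completing the 9-week program", with 3 days in both arms at that later point. The section on the TR intervention calls the initial hospital stage one week.
- **Primary hypothesis sample size considerations** assumes that the mean difference in days alive and out of hospital (DAOH) for the "TRG arm and the CG arm is 21 days with a common standard deviation in each arm of 100", and allows for 5% loss.

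**The concern.** Worst and best case are normally read together as a range: if the conclusion is the same under both, missing data cannot overturn it. That holds for a single arm. For a comparison, applying the same extreme to both arms largely cancels when the arms lose similar numbers. Agreement between the two analyses then says little about the treatment effect. In an open-label trial where one arm trains five times a week, the reasons for leaving may differ by arm, and that is the case the scenarios should test.

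Rule 1 has a different weakness. It treats the observed period as representative of the year. In ITT the observed period opens with a required hospital stay that is longer in TR. For an early dropout, that stay is a large share of the time observed and is scaled up with it. Rules 1 and 3 also give a dropout no chance of dying after leaving.

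**Working it through.** **The plan's own figure.** With a 21-day difference, a standard deviation of 100, two-sided 0.05 and 80% power, n per arm = 2 × (1.960 + 0.842)² × (100/21)² ≈ 356. Dividing by the Wilcoxon relative efficiency gives 373 (0.955, normal data) or about 412 (0.864, lower bound). The stated 400 lies in that range, and 800/0.95 = 842. The design reproduces.

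**Bounds on the difference.** Inputs: 5% loss from the sample size section, assumed equal by arm; dropout day d, which the protocol does not give, varied from 30 to 270; a 365-day scale, as in the rules. Moving one arm from best to worst case changes its mean by 0.05 × (365 − d). The same rule in both arms cancels. Crossed rules shift the difference by the full amount in either direction.

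| Dropout day | Same rule in both arms | Crossed rules (days) |
|---|---|---|
| 30 | about 0 | ±0.05 × 335 = ±16.75 |
| 63 | about 0 | ±0.05 × 302 = ±15.1 |
| 180 | about 0 | ±0.05 × 185 = ±9.25 |
| 270 | about 0 | ±0.05 × 95 = ±4.75 |

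A simulation with no treatment effect (421 per arm, 5% loss per arm, dropout between days 10 and 120, 400 replicates, required stays not counted) agrees. The mean difference was −0.3 days with worst case in both arms, −0.2 with best case in both, and −15.1 and +14.7 when crossed. The planned Wilcoxon test was significant in 5.8% of runs under either same-direction rule and in 48% and 51% under the crossed ones. Those rejection rates depend on simulated event rates that the protocol does not give; the mean shifts follow from the formula above.

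With unequal loss (assumed 7% TR, 3% control, day 63), relative to best case in both arms:

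- worst case in both arms: −(0.07 − 0.03) × 302 = −12.1 days
- TR worst, control best: −0.07 × 302 = −21.1 days
- TR best, control worst: +0.03 × 302 = +9.1 days

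The same-direction pair spans −12.1 to 0. The crossed range is −21.1 to +9.1.

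**Rule 1 and the entry stay (ITT, required stays counted, no other hospital days).** Imputed value = (d − stay)/d × 365.

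- Day 30, TR: 25/30 × 365 = 304.2. Control: 27/30 × 365 = 328.5. Gap 24.3 days.
- Completers: TR 365 − 5 − 3 = 357. Control 365 − 3 − 3 = 359. Gap 2 days.
- Excess in the mean difference at 5% equal loss: 0.05 × (24.3 − 2) = 1.1 days against TR.
- Day 63: 336.0 versus 347.6, gap 11.6, excess 0.05 × 9.6 = 0.5 days.
- With a 7-day TR stay the excess is 0.05 × (48.7 − 4) = 2.2 days at day 30 and 0.05 × (23.2 − 4) = 1.0 at day 63.
- With unequal loss (assumed 7% TR, 3% control, day 30, 5-day stay): 0.07 × (357 − 304.2) − 0.03 × (359 − 328.5) = 3.7 − 0.9 = 2.8 days against TR.

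**No death after dropout (rules 1 and 3).** With constant hazard λ and T = 365 − d, the days over-credited per dropout are T − (1 − e^(−λT))/λ. At an assumed 10% annual mortality this is 15.7 days at day 30 and 12.8 at day 63, or 0.8 and 0.6 days in the arm mean at 5% loss. For 5% to 20% annual mortality the day-30 figure runs from 7.8 to 32.1 days per dropout.

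**The case against.** The sponsor can fairly say that crossed scenarios and tipping-point analyses are commonly left to a SAP, which is not shown, and that the rules' silence on arm leaves room for them. That is right as far as it goes: their absence alone would be no finding. The point concerns the worst and best cases that the protocol does write down, whose natural reading applies each to every dropout and so does not test the comparison.

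It can also be said that crossed scenarios are extremes that nobody believes. That is true of any bound, and it is why a tipping-point analysis is an acceptable alternative.

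On rule 1 the objection is stronger, and most of it stands. The effect needs required stays to count, which the text implies only by not excluding them. It is confined to ITT, because MITT follow-up starts after the entry stay. At 5% equal loss it is small. Counted stays do more harm through the endpoint itself. In simulated trials with no treatment effect and stays of 5 + 3 days versus 3 + 3 counted for everyone, the Wilcoxon test was significant in every run even with complete data. A reader might therefore infer that rule 1 produces a large spurious advantage for control. The documents do not support that: such a result needs stays counted for dropouts but not for completers, together with markedly higher early withdrawal in TR, and neither is in the protocol.

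A reader might also take a patient lost at day 400 as a gap in the rules. Under Primary Outcome, which uses the first 365 days, that patient is complete. Under the sample size section, which divides by total follow-up, the ratio can still be computed. The awkwardness comes mainly from the conflict between those two sections.

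**Conclusion.** The concern holds in a limited form. The worst-case and best-case rules bound patient values and arm means but leave the treatment difference unbracketed. At the planned loss the unexamined range is about ±15 days for early dropout, and ±5 to ±17 across dropout days 270 to 30, against a 21-day design effect. The listed scenarios can therefore agree while the conclusion still depends on the missing data. This rests on equal 5% loss, assumed dropout days and a 365-day scale; the protocol does not tie its 21 days to a window.

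The entry-stay extrapolation in rule 1 is real under the literal wording but secondary: about 0.5 to 2 days in the ITT mean difference at equal loss, more if early withdrawal is higher in TR, and none from the entry stay in MITT.

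Two broader readings should be resisted. The rules as a set do not assume zero mortality after dropout: rules 1 and 3 do, but rule 2 counts every missing day as lost. Nor do they fail to bound anything: only the between-arm difference escapes.

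**What to change.** - Add crossed scenarios (TR worst with control best, and the reverse), or a tipping-point analysis, to the same-direction ones.
- State that protocol-required stays are excluded from numerator and denominator for all patients, completers included, and before any extrapolation. Reconcile the 5-day and one-week descriptions of the TR entry stage.
- Name one rule as primary. Align its 365-day trigger and scale with the endpoint window once Primary Outcome and the sample size section agree on that window.
- Add, as a sensitivity analysis, an imputation that allows death after dropout. Removing the stays alone is not enough: an event-free dropout is then credited the full 365 days under rule 1, which tilts towards whichever arm loses more patients. Making such an imputation the primary analysis is a judgement for the sponsor and is not required here.

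The cost is protocol or SAP wording and programming, with no new data. The downside is a wider and less reassuring sensitivity range.

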### 331 Subgroup and Sensitivity Analyses

332 Subgroup analyses will be conducted to assess treatment heterogeneity by study site, age, sex,  
333 baseline NYHA class, peak VO2 consumption and duration of follow-up. An additional sensitivity  
334 analysis will be conducted excluding patients from the control arm if they participated in a  
335 rehabilitation program.

### 336 Secondary Outcomes Assessed at 12 months.

337 The following time-to-event outcomes will be illustrated using Kaplan-Meier plots and  
338 compared between treatment arms using Cox proportional hazards regression with site and treatment  
339 arm as covariates: all-cause mortality, CV mortality, all-cause hospitalizations, CV hospitalizations,  
340 HF hospitalization, composite of all-cause mortality or all-cause hospitalization, composite of all-  
341 cause mortality or CV hospitalization, composite of all-cause mortality or HF hospitalization and  
342 composite of cardiovascular mortality or HF hospitalization. All available follow-up will be used with  
343 event rates estimated at 12 months.

### 344 Tertiary Outcomes Assessed at 9 weeks.

345 The following continuous outcomes will be compared between treatment arms using analysis  
346 of variance adjusting for baseline level of the outcome measure and site: change in CPET duration,

347 change in pVO2 in CPET, change in pVO2%N in CPET, change in 6-MWT distance, change in QoL  
 348 measures with the SF-36 instrument as well as change in depression and anxiety scales. NYHA class  
 349 will be analyzed as ordinal variable using ordinal logistic regression including terms of baseline  
 350 NYHA class, site and treatment arm.  
 351 The summary is included in the **Table 7 and Table 8.**

352 **Table 7. TELEREH-HF Endpoints**  
 353

Primary end-point:
 
The percent of number of days alive and out of hospital (DAOH) during the 12-24 months follow-up

Secondary end-points:
 
Secondary outcomes assessed at 12-24 months:
 
 
- all-cause and CV mortality
 
- all-cause, CV and HF hospitalization
 
 
Tertiary analysis - outcomes assessed at 9 weeks - the effectiveness of hybrid TR based on:
 
 
- New York Heart Association class
 
- cardiopulmonary exercise treadmill test duration
 
- peak oxygen consumption (pVO2)
 
- percentage of predicted peak oxygen consumption (pVO2%N)
 
- six-minute walking test distance
 
- quality of life assessment
 
- depression assessment
 
- anxiety assessment
 
- acceptance of TR
 
- adherence to TR
 

Composite end-points encompasses:
 
 
- CV mortality and HF hospitalization
 
- CV mortality and CV hospitalization
 
- CV mortality and non CV hospitalization
 
- all-cause mortality and CV hospitalization
 
- all-cause mortality and non CV hospitalization
 

354 TRG-telerehabilitation group, CG-control group, CV-cardiovascular, HF-heart failure, TR-telerehabilitation  
 355  
 356  
 357  
 358  
 359  
 360  
 361  
 362  
 363  
 364

365  
 366  
 367  
 368  
 369  
 370  
 371  
 372

**Table 8. Definitions of Outcomes**

Hospitalization
 
Regarding this trial, hospitalization is defined as hospital admission resulting in an overnight stay where the length of stay is at least 24 hours. In case of emergency room visits that include a date change with an unclear length of stay the (Clinical Endpoint Committee) CEC members are requested to discuss these events at a CEC meeting where the final classification (ambulatory visit versus hospital stay) will be made. All other events leading to an emergency room visit with a length of stay under 24 hours will be not classified as hospitalization.


Primary reason of hospitalization
 
I. Non-cardiovascular reason for hospitalization
 
For a hospitalization considered as non-cardiovascular the admission reason should be clearly not associated with a deterioration of a cardiovascular condition. Examples are: admission due to a fall, back pain or others.
 
II. Cardiovascular reason for hospitalization
 
For a hospitalization considered as cardiovascular the admission reason should be clearly associated with a deterioration of a cardiovascular condition or need of intensified diagnostic procedures only feasible in a hospital. Examples could be: newly occurred or recurrent arrhythmia, acute coronary syndrome, myocardial infarction, worsening of heart failure, myocarditis, endocarditis, stroke or pulmonary infarction with the need for intensified diagnostic and therapy. The admission reason should be determined in the evaluation form. Hospitalisation for or with worsening heart failure
 
1. A cardiovascular hospitalisation will be classified as ‘for or with worsening heart failure’ if the reason for admission is worsening heart failure. The CEC diagnosis will be made using the criteria described below, irrespective of the investigator and/or discharge diagnosis.
 
The following two criteria must apply to adjudicate ‘worsening heart failure’:
 
a. Presence of 2 typical heart failure signs or symptoms (including shortness of breath, dyspnoea on exertion, paroxysmal nocturnal dyspnoea, orthopnoea, bendopnea, fatigue, reduced exercise tolerance, pulmonary oedema, jugular vein distensions, pulmonary rales, S3 on cardiac auscultation, hepatojugular reflux, altered haemodynamics, peripheral oedema, and cardiomegaly).      OR objective evidence for worsening heart failure (as revealed by echocardiography, chest radiography or measurement of a natriuretic peptide) and an intensification of heart failure therapy).
 
b. Treatment for heart failure started or intensified:
 
To fulfil this criterion, the patient must have an initiation or intensification of therapy for heart failure, including at least one of the following:
 
 
- Augmentation in oral diuretic therapy
 
- Intravenous diuretic or vasoactive agent (e.g. inotrope, vasopressor or vasodilator)
 
- Mechanical circulatory support or mechanical fluid removal
 
 
For the avoidance of doubt, if the patient developed worsening heart failure during a hospitalisation (but heart failure was not the reason or a major component of the respective hospital admission), this will not be judged a 'Hospitalisation for or with worsening heart failure', but should be discussed in a CEC meeting.


Death
 
For this trial, death is defined as death of any cause within a hospital or outside of a hospital. For secondary endpoint, the death will be distinguished in cardiovascular and non-cardiovascular death. If it is not possible to evaluate the cause of death, the CEC members are requested to discuss these

events at a CEC meeting where the final classification will be made.

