### 117 **Intervention in Telerehabilitation Group**

118 The TR group patients will undergo a 9-week hybrid comprehensive TR program consisting of  
119 two stages: an initial stage (1-week) conducted at hospital and a basic stage 8-week home-based TR

120 five times weekly. The goals of the initial stage are: a baseline clinical examination, optimization of  
121 treatment, education, individual planning of exercise training and performing five monitored  
122 educational training sessions. The basic stage, which is conducted at home consisted of two parts, is  
123 performed prior to each training session: the first part - the training consent procedure is required for a  
124 patient to access each training session, and the second part - the training session.

125

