### 311 **Statistical Analyses**

#### 312 Primary Outcome

313 The primary analysis will be based on the percent of DAOH during the 12-24-month follow-  
314 up and analyzed using the Wilcoxon-Mann-Whitney test. DAOH is defined as the number days out of  
315 the first 365 days of follow-up that the patient was alive minus the total number of days the patient  
316 spent in the hospital (sum of days spent in the hospital for each hospitalization). Fractions of days  
317 spent in the hospital will be rounded up to full days. We plan to conduct two analyses, intent-to-treat  
318 (ITT) and modified intent-to-treat (MITT). The follow-up for ITT will start at randomization and  
319 extend for a minimum of about 14 months (9 week training period and 12 month follow-up) and a

320 maximum of 26 months (9 week training period plus 24 months of follow-up). For the MITT analysis,  
321 the follow-up will start at the end of the 9-week period.

322

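### DAOH and all-cause hospitalization count every overnight stay, so inpatient rehabilitation in controls, if it occurs, would be scored as a bad outcome; one symmetric rule on planned stays is needed

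*Protocol*

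**What the plan says.** Protocol, Table 8 (Hospitalization): "hospitalization is defined as hospital admission resulting in an overnight stay where the length of stay is at least 24 hours". Emergency-room visits are the only borderline case singled out for a committee decision; planned or rehabilitation admissions are not mentioned.

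Protocol, Statistical Analyses, Primary Outcome: DAOH is reduced by the days "spent in the hospital (sum of days spent in the hospital for each hospitalization", again without exemption. Two analyses are planned. They are introduced with the words "ITT) and modified intent-to-treat (MITT). The follow-up for ITT will start at randomization and" so the ITT window includes the 9-week period. For MITT, "the follow-up will start at the end of the 9-week period".

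Protocol, Control Group: usual care follows each centre's own standard, and some controls can "participate in a rehabilitation program and some of them has remote monitoring of CIEDs". Setting, share and duration are not given.

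The TR arm also spends planned time in hospital. The intervention section describes "two stages: an initial stage (1-week) conducted at hospital and a basic stage 8-week home-based TR". Under Clinical examinations, the entry stay is 5 days for TR against 3 for controls: "hospitalization-TRG, and 3 days of hospitalisation-CG) and after completing the 9-week program". The week-9 stay is 3 days in both arms.

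Protocol, Subgroup and Sensitivity Analyses: an "analysis will be conducted excluding patients from the control arm if they participated in a" rehabilitation programme.

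**The concern.** The trial moves rehabilitation from hospital to home. If a control has the same kind of treatment as an inpatient, the stated rules take every one of those days off DAOH. They also record an all-cause hospitalization, although the patient has not deteriorated. The TR patient's 8 weeks of home training cost nothing. A difference in DAOH could then reflect where rehabilitation took place and not health or prognosis.

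The Wilcoxon-Mann-Whitney test makes this more than a nuisance. Patients without any hospital day tie at the top of the scale. One planned stay of two or three weeks drops a well patient from that tie to near the bottom, so a small share of such patients can move the test while the mean hardly changes.

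**Working it through.** **The plan's own figures.** n per arm = 2(1.96 + 0.84)² × 100² / 21² = 356 for a z test, and power at 400 per arm is 84.4%. With an asymptotic relative efficiency of 0.955 for the rank test, power is 82.7%; at the minimum of 0.864 it is 78.8%. The stated 80% lies within this range, and 800/0.95 = 842.1 matches 842. The sample size is not in dispute.

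**Inputs from the protocol.** Two-sided 0.05, 400 evaluable per arm, design difference 21 days, the hospitalization and DAOH rules, and entry stays of 5 and 3 days.

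**Assumptions, because the protocol gives no figure.** f is the excess share of controls over TR patients with an inpatient rehabilitation stay; L is its length in days. There is no true effect, follow-up is 365 days, 8% die (uniformly over the year), and 30-50% have an illness admission (lognormal, median 9 days, log-SD 0.9). Study-mandated stays are left out.

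**Result.** Mean shift = f × L. The last column is the simulated rate of significant results favouring TR.

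| f | Mean shift, L = 14 to 21 days | False 'TR better' |
|---|---|---|
| 0 | 0 | about 2.5% (nominal) |
| 2% | 0.28 to 0.42 days | about 4-7% |
| 4% | 0.56 to 0.84 days | about 11-14% |
| 8% | 1.12 to 1.68 days | about 27-43% |

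A second set-up (14-26 months of follow-up, 10% deaths, L of 14-28 days) gave 5-7% at f = 2%, 11-18% at 5%, 23-40% at 8% and 86-98% at 20%. The mean shift stays far below the design difference: reaching 21 days at L = 28 would need f = 21/28 = 75%.

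**Hand check at f = 8%, L = 21, 30% admitted.**
- Share with no lost day: 0.92 × 0.70 = 0.644. Their mid-rank position is 1 − 0.644/2 = 0.678.
- Share losing more than 21 days: deaths 0.08 × 344/365 = 0.075, plus survivors with a long admission 0.92 × 0.30 × 0.173 = 0.048, total 0.123. Here 0.173 is the lognormal tail beyond 21 days.
- A top-tied control with a rehabilitation stay therefore falls by 0.678 − 0.123 = 0.555.
- Shift in the pairwise win probability from these patients alone: 0.08 × 0.644 × 0.555 = 0.0286.
- Null standard error with ties: √[(1/12)(2/400)(1 − 0.644³)] = 0.0175, so z = 1.63.
- Chance of a significant result: P(Z > 1.96 − 1.63) = about 37%, inside the simulated range.

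**Study stays counted as well.** Adding 5 days to every TR patient and 3 to every control breaks the large tie against TR. In the 365-day set-up with L = 21, false 'control better' is then about 78-100% for f up to 15%. In the longer set-up it is about 100% at f = 0 and at f = 8%, and 54% at f = 20%. At f = 40% the result flips to 68% false 'TR better'.

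**Planned exclusion of rehabilitated controls.** At f = 20% the simulated error was 2.7% favouring TR and 2.0% favouring control, but only because uptake was generated at random. Real uptake need not be.

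**The case against.** A reader might infer that the comparator's treatment is in fact scored against it, so that DAOH is biased toward TR. The protocol does not support that, for four reasons.

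- **Setting.** It never says that control rehabilitation is inpatient. Outpatient or home programmes would not meet Table 8 and would cost no DAOH. The 8% in the Introduction is national availability of cardiac rehabilitation of any kind; it is neither an inpatient share nor an excess of controls over TR.
- **Timing.** Control rehabilitation is mentioned while describing care up to week 9; nothing says that it continues through 12-24 months. Stays that end before week 9 fall outside the MITT window. TR patients receive usual care too, so a control excess after week 9 is an assumption.
- **Direction.** TR's hospital stage meets the same definition. Under ITT as written, the error can run against TR.
- **Reach.** Table 8 ties a cardiovascular admission to deterioration or to diagnostics only feasible in hospital, and requires the reason to be recorded. The cardiovascular and HF hospitalization endpoints are therefore largely protected. The exposure is in DAOH, all-cause hospitalization and the composites that use all-cause or non-cardiovascular admissions.

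All four points stand and limit the claim. Two further arguments stand in part. The planned sensitivity analysis shows that control rehabilitation was foreseen, but it is not primary and it removes patients from one arm on a post-randomization event, so it gives up the randomized comparison. Counting all hospital days is also a coherent meaning of DAOH, which is why that version should be kept. It cannot, however, separate better health from a change in the place of treatment.

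**Conclusion.** The gap in the definitions is real; the bias is conditional. Table 8 and the DAOH rule do not separate planned rehabilitation admissions from admissions for illness, and the protocol permits control rehabilitation in any setting. If an excess of inpatient stays occurs in controls, the rank test is sensitive to it: false 'TR better' of about 4-7% at a 2% excess, 11-14% at 4% and 27-43% at 8%. These figures assume no true effect, 400 per arm, 14-21 day stays and no study stays counted. Neither the share nor the length is in the protocol, so they show sensitivity and are not an estimate for this trial.

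The net direction under ITT is not determined by the text, because TR's hospital stage counts against TR. Two opposing artefacts do not make the endpoint sound. Exempting only the study stays would leave the one described here, and MITT would still count any control rehabilitation after week 9. The planned one-arm exclusion does not cure it.

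**What to change.** State one rule, identical in both arms, in the Primary Outcome section and in Table 8: planned rehabilitation admissions and protocol-mandated stays, including TR's in-hospital stage, count neither as hospital days nor as hospitalization events. With f = 0 and study stays out, the simulated two-sided error returns to about 5% (4.6-5.9%).

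- Identify protocol stays from the study schedule, so that the blinded Clinical Endpoint Committee is not shown them. Let the committee classify only other planned rehabilitation admissions, as one added category on its evaluation form. The one-week and 5-day descriptions of TR's initial stay should be reconciled so that the schedule is unambiguous.
- Report the number and days of exempt stays by arm.
- Keep the all-days DAOH as a labelled sensitivity analysis.
- Use this comparison of all randomized patients to address control rehabilitation stays, and do not rely on the one-arm exclusion.

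The cost is one committee category and a sentence or two of definition. The downside is small but real: the exempt days are truly days away from home, and the retained all-days analysis shows their effect.
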